## 11.0 Statistical Analyses Plan:

All outcomes will be summarized and described with appropriate summary statistics. For example, estimated binomial proportions (e.g., for % of HCV-infected hepatocytes) will include 95% confidence intervals. Means, medians for continuous outcomes will include confidence

intervals and key percentiles (eg, 25th, 75th percentiles), respectively. Outcomes defined as changes will also present summary distribution of values at each time point contributing to change outcome. In addition, because of small sample size, outcomes will also be summarized on a per-subject basis for reporting. Changes will be defined as absolute differences for those outcomes where baseline distribution of proportion is close to 0 or 1, and relative (and absolute secondarily), changes otherwise. For continuous outcomes, both absolute and relative changes from baseline will be explored and summarized. Confidence intervals (using exact methods) on change outcomes will be calculated and presented.

For the primary outcome, the estimated differences will be summarized and described on a per-subject basis (i.e. 15 differences and intra-subject confidence intervals). Additionally, the proportion of infected hepatocytes will be summarized across subjects at each time point and presented. Finally, the average difference from week 0 to week 1 (absolute difference) for the study sample will be estimated and summarized.

For the plasma VK secondary outcome, longitudinal modeling will be used to combine plasma HCV viral loads (VL) over the first week. For instance, marginal modeling will focus on estimation of levels across the study sample (ie, population level inference). This can be used to describe the average change in HCV VL over the first week on treatment. In addition, (generalized linear) mixed effects models will focus on subject-specific inference (ie, prediction). Since this is a small study, these data will be graphically represented by subject.

Associations between two continuous outcomes will be described using rank-based (e.g., Spearman, using exact method versions with PROC STATXACT [specifically PROC ASSOCIAT]) correlations (and will be presented graphically using scatterplots), and associations between a continuous and a categorical outcome will be summarized by separately summarizing distribution of the continuous outcome by the other covariate category (level), as well as testing for differences in the distribution of the continuous covariate by varying levels of the categorical covariate using the exact version of Kruskal-Wallis test (equivalent to the exact version of Wilcoxon rank sum tests for more than two categories). For restricted alternatives of monotonicity among more than two groups, additional statistical tests such as Jonckheere-Terpstra may also be used.

Contingency tables will describe ordinal fibrosis staging (non-continuous outcomes), and distributions of continuous outcomes will be summarized by fibrosis stage, as necessary.

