### 3.2 Secondary Objectives:

3.2.1. Estimate the change over the first week in plasma HCV RNA in subjects with HCV mono-infected and HIV/HCV co-infected participants on therapy with two or three DAAs

3.2.2. Estimate the 1 week change in the amount of HCV RNA per infected hepatocyte using scLCM on liver biopsy specimens, obtained just prior to treatment initiation (pre-treatment), and after the first week of DAA therapy.

3.2.3. Estimate the change in the proportion of HCV-infected hepatocytes that express interferon-stimulated genes (ISGs) within the first week of DAA therapy using scLCM.

3.2.4. Measure the change in expression of ISGs in non-parenchymal intrahepatic immune cells (Kupffer cells, plasmacytoid dendritic cells) within the first week of DAA therapy using scLCM.

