### 5.1 Inclusion/Exclusion criteria

#### Inclusion Criteria

Participants must meet all of the following inclusion criteria to be eligible for participation

1. Ability and willingness of participant to provide written informed consent.
2. Men and women age  $\geq 18$  to  $\leq 70$  years at study entry
3. Body mass index (BMI)  $\geq 18$  kg/m^2
4. HCV RNA  $\geq 10,000$  IU/mL at Screening
5. HCV genotype 1a at Screening or within 6 months of screening
6. Chronic HCV infection ( $\geq 6$  months) documented by prior medical history
7. HCV treatment-naïve with no prior treatment with any IFN, RBV, or approved or experimental HCV-specific DAA
8. Absence of cirrhosis as defined as transient elastography (FibroScan®) liver stiffness measurement  $< 12.5$  kPa within 6 months of screening
9. The following laboratory values obtained within 42 days prior to study entry.

- Hemoglobin > 10 g/dL for men and > 9 g/dL for women
- Platelet count  $\geq 90,000/\text{mm}^3$
- International normalized ratio (INR)  $\leq 1.5$
- Calculated creatinine clearance (CrCl)  $\geq 30$  mL/min
- Alanine aminotransferase (ALT) and aspartate aminotransferase level  $\leq 10$  x upper limit of the normal range (ULN)
- Total bilirubin <3 mg/dL
- Albumin  $\geq 3.5$  g/dL
- CD4+ cell count  $\geq 200$  cells/uL and CD4+ cell percentage  $\geq 14\%$  within 42 days of study entry at any US laboratory that has a Clinical Laboratory Improvement Amendments (CLIA) certification [HIV seropositive participants only]
- HIV RNA < 400 copies/mL prior to study entry by any US laboratory that has a CLIA certification or its equivalent [HIV seropositive participants only]

10. On a qualifying antiretroviral therapy (ART) regimen which is permitted with SOF/VEL. This allows for antiretroviral regimen that does not include Efavirenz, Nevirapine, or Tipranavir.

11. Women of childbearing potential must have a negative serum pregnancy test at Screening and a negative urine pregnancy test on Day 0 prior to liver biopsy

12. All participants must agree not to participate in a conception process (e.g., active attempt to become pregnant or to impregnate, sperm donation, in vitro fertilization).

13. If participating in sexual activity that could lead to pregnancy, the participant (men and women) must also agree to use two reliable methods of contraception simultaneously while receiving study treatment and for 30 days after stopping study treatment.

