#### 8.4 Plasma Viral Kinetics (VK)

Plasma for VK will be collected for HCV RNA measurements at entry/day 0 (intensive sampling) and days 1, 2, 3, 4, and 7.

Upon admission to the inpatient research unit on Day 0, a peripheral IV will be placed or phlebotomy performed and the predose VK sample will be collected. After CNB1 is performed on entry/day 0, participants will be immediately returned to the inpatient unit and will receive a standardized meal. About 30 minutes after the meal is given, study drug will be administered. HCV RNA and plasma immunology measurements will be timed based on DAA administration, with DAA administration being considered Hour 0 for the VK portion of the study. Thereafter, intensive VK sampling over 24 hours will be conducted, with post-dose samples being collected at 4h, 6h, 12h, 18h, and 24h after drug administration.

After the 24-hour intensive plasma VK measurements are completed (on day 1), participants will be administered DAAs for day 1 and discharged to home. Thereafter, they will return daily for phlebotomy on days 2, 3, and 4 timed in relation to the intensive plasma VK samples performed on entry/day 0. Samples will be timed so that they are obtained  $24 \pm 2$  hours from the first administered dose of study drugs on entry/day 0 if this is possible based on the subject schedule. Phlebotomy will be performed for plasma VK (HCV RNA) measurements and plasma immunology measurements. DAA will be administered after phlebotomy on days 2, 3, and 4.

On day 7, participants will undergo phlebotomy for plasma VK (HCV RNA) measurements and plasma immunology measurements.

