## 10.0 Sample Size

The anticipated sample size for analyses is 15 participants with 5 in each of three distinct groups. Group C will enroll 5 patients with HIV/HCV genotype 1a coinfection and will receive treatment with SOF/VEL representing inhibitors of HCV NS5B and NS5A a. Group A and B will

each enroll 5 patients with HIV genotype 1a mono-infection; Group A will be treated with SOF/VEL/VOX and Group B will receive only SOF/VEL representing inhibitors of HCV NS5B and NS5A only. As such, Groups B and C are treated with same two-drug DAA regimen and will permit the comparison of persons with HIV/HCV and HCV. In contrast, Groups A and B include patients with HCV mono-infection and differ by the use of the HCV NS3/4 inhibitor Voxilaprevir in Group A and will permit the comparison of the NS3/4 inhibition versus none.

Because this study is exploratory and is enrolling a very small sample, traditional statistical power calculations are not being used to justify the sample size. Instead, this sample size was developed based on the feasibility of both anticipated enrollment and the feasibility of the laboratory procedures, namely single cell laser microdissection.

For the primary outcome of difference in proportion of HCV-infected hepatocytes between week 1 and baseline, we present an approximate confidence interval around the difference in proportion within subject to show the level of precision in this exploratory single-arm study. The following assumptions are made to approximate the confidence interval in a conservative way:

- for within-subject variation – proportion of infected hepatocytes at any particular time-point is 50% (this assumption is conservative as results in maximum variation),
- the number of hepatocytes measured within each subject is 400 (this is conservative as it is estimated that between 400 and 1000 hepatocytes will be measured),
- normal approximation to the binomial for standard error estimation, and the variance of the difference will be approximated as twice the variance (assuming independence between week 1 and baseline, which is conservative except under negative correlation, which is not expected given the reported potency of the intervention being studied).

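### Section 11 names absolute and relative change, but no log scale, for plasma HCV RNA; after a fall of 2 log10 or more, absolute change in IU/mL mainly restates baseline load

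*Combined protocol and SAP*

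**What the plan says.** Secondary objective 3.2.1 reads: "Estimate the change over the first week in plasma HCV RNA in subjects with HCV mono-infected and HIV/HCV co-infected participants" on two or three DAAs. It names no measurement scale. Section 8.4 sets the sampling: "Plasma for VK will be collected for HCV RNA measurements at entry/day 0 (intensive sampling) and days 1, 2, 3, 4, and 7", with post-dose samples at 4, 6, 12, 18 and 24 hours on the first day.

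Section 11 gives one rule for all continuous change outcomes: "For continuous outcomes, both absolute and relative changes from baseline will be explored and summarized". It asks for means and medians with confidence intervals and percentiles, for the distribution of values at each time point, and for per-subject summaries. For plasma it adds that "longitudinal modeling will be used to combine plasma HCV viral loads (VL) over the first week". Of the marginal model it says: "This can be used to describe the average change in HCV VL over the first week on treatment". Generalized linear mixed models are planned as well, with response scale, link and distribution unstated. Associations between a continuous and a categorical variable are to be tested by exact Kruskal-Wallis or Wilcoxon methods.

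The only viral load figure among the eligibility criteria (Section 5.1, criterion 4) is "HCV RNA $\geq 10,000$ IU/mL at Screening", with no upper limit. On group size, Section 10 says: "The anticipated sample size for analyses is 15 participants with 5 in each of three distinct groups".

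The plan mentions no log10 response, log link or log reduction for plasma HCV RNA, and no quantification limit or rule for results below one.

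**The concern.** Viral load responds to treatment multiplicatively. A subtraction in IU/mL after a large fall gives back almost the whole starting value, whatever remains. A percentage change crowds towards -100%, so responses that differ tenfold in residual virus look alike.

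Section 10 sets out two comparisons: three drugs against two in mono-infection (Group A against B), and mono-infection against HIV coinfection on the same two drugs (Group B against C). With five participants per group and no ceiling on baseline load, a mean absolute change would be governed by whoever entered with the most virus. Leaving the scale open until the data are in also allows the scale to be chosen after seeing which one separates the groups.

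**Working it through.** **The plan's own figure.** The documents give no precision or effect figure for the plasma outcome. The one precision figure, in Section 10, concerns the primary outcome, and it reproduces: √(2 × 0.5 × 0.5 / 400) = 0.0354; 0.0354/√5 = 0.0158; 1.96 × 0.0158 = 0.031. It says nothing about plasma.

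**Algebra.** For baseline B and a fall of L log10:
- absolute change = -B × (1 - 10^-L)
- relative change = -(1 - 10^-L)
- log10 change = -L

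| Fall (log10) | Absolute change from B = 1,000,000 IU/mL | Relative change | Residual (IU/mL) |
|---|---|---|---|
| 1 | -900,000 | -90% | 100,000 |
| 2 | -990,000 | -99% | 10,000 |
| 3 | -999,000 | -99.9% | 1,000 |
| 4 | -999,900 | -99.99% | 100 |

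Between falls of 2 and 4 log10 the residual virus differs 100-fold, while both named measures move by about 1%. Conversely, 50,000 to 50 and 5,000,000 to 5,000 are the same 3-log10 response, but the absolute changes are -49,950 and -4,995,000, a 100-fold difference.

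**Simulation inputs.** From the documents: 5 per group and the 10,000 IU/mL floor (4 log10). Assumed: baseline log10 mean 6.0 and SD 0.7; mean declines of 4.0 and 3.0 log10; decline SD 0.4. There were 20,000 trials, tested two-sided at 5%.

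| Scale | Groups ordered wrongly by mean | t-test power | Exact rank test power |
|---|---|---|---|
| Absolute (IU/mL) | about 50% | 2% | about 3% |
| Relative | under 0.1% | 60% | 86% |
| log10 | under 0.1% | 93% | 86% |

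The correlation of absolute change with baseline is -1.00 to two decimals. The 3% rank-test rate is no power at all: with 5 versus 5 the exact two-sided test rejects in 8 of 252 arrangements, and 8/252 = 3.2% is its rate under no difference. Mean relative changes are -99.98% and -99.85%.

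**Range.**
- Decline SD 0.3 to 0.5: t-test power falls from 85% to 38% on relative change and from 99.5% to 79% on log10 change. The exact rank test falls from 98% to 68% on both. Absolute change stays at 2% by t-test.
- A 0.5-log10 difference at SD 0.4: t-test power is 2% (absolute), 25% (relative) and 41% (log10); the rank test gives 31% on both relative and log10 change.
- Shallower declines of 2.5 and 1.5 log10: 2%, 59% and 93% by t-test.
- No true difference: the larger group mean absolute change is typically 2.3 times the smaller.

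**The case against.** The strongest reply is that Section 11 is silent on the scale rather than wrong. It says changes will be explored, introduces the marginal model only as an example, and leaves the link and response of the mixed model open. A log10 response or a log link would fit that text, and a log10 difference is itself the log of a ratio. This stands. A reader might infer that the models will be fitted to raw IU/mL and driven by the highest baselines, but the documents do not say so.

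Second, relative change is monotone in log change. The exact rank tests that Section 11 does plan lose nothing on it, and with five per group the median relative change converts directly to the median log10 change. The t-test used above is not in the plan; it serves only to measure information lost in a mean. A reader might therefore conclude that a real difference would be nearly invisible on both named scales. That is unsupported: it holds for absolute change but not for relative change.

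Third, per-subject summaries, values at each time point and graphs by subject would let a careful reader recover log declines for 15 people. This limits the harm but does not repair group means, their confidence intervals or a model on the wrong scale.

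Fourth, the study is exploratory, makes no power claim, and its primary outcome is untouched. That bears on the importance of the point, not on whether it is correct.

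**Conclusion.** The point holds in a limited form. Of the two change measures named, absolute change in IU/mL does not measure response once the fall reaches 2 log10, and the rank tests do not rescue it. Mean relative change loses precision (60% against 93% t-test power in the base case) but keeps the ordering. Whether the longitudinal models are affected depends on a scale that the plan leaves unstated.

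The conclusion rests on a multi-log first-week plasma fall and on a wide baseline spread. Both are assumptions: the documents supply only the 10,000 IU/mL floor. Two further readings go too far:
- That every participant sits at -99% or beyond. This needs at least 2 log10 in everyone and need not apply to the samples in the first 24 hours. Under a second set of assumed inputs (baseline log10 mean 6.2, falls of 3 and 4 or 2.5 and 3.5 log10, SD 0.5), 92% to 99% of participants reached it.
- That the same argument covers HCV RNA per infected hepatocyte (objective 3.2.2). Section 8.8 reports 1 to 50 IU per cell, mostly below 10, so the multi-log argument does not carry over.

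This is a secondary outcome, and the change is worth making before analysis because it removes a free choice at almost no cost.

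**What to change.** In Section 11, for objective 3.2.1:
- Define the outcome as change in log10 HCV RNA (IU/mL) from the Day 0 pre-dose sample.
- Fit the marginal and mixed models to log10 HCV RNA.
- Report group declines as log10 changes (ratios of geometric means) with confidence intervals.
- State the assay's quantification limit and treat results below it as left-censored, not as zero or missing.
- Keep absolute change in IU/mL as a listing only.

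The cost is a few lines of SAP text and slightly more programming for the censored likelihood. No samples, visits or participants are added.

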These assumptions give an estimated within-subject standard error of 0.035 for the primary outcome and can be used to formulate a confidence interval on the difference in proportions of HCV-infected hepatocytes between week 1 and baseline on a single individual. For other less conservative assumptions (larger number of hepatocytes sampled, or estimated proportion of HCV-infected hepatocytes being either larger or smaller than 0.5 at either week 1 or week 0), the within subject standard error for the difference in proportions outcome would be smaller than 0.035, and so this represents the maximum standard error for the given assay parameters that specify that at least 400 hepatocytes will be measured in each subject at each time point.

For combining the estimated differences across subjects in order to obtain a study sample estimate for the difference in proportion of HCV positive hepatocytes between week 1 and baseline, the average difference across the 5 subjects within each group will be calculated. Assuming independence across individuals, and using the above maximum within subject standard error for each of the 5 subjects gives a standard error for the average as  $0.035/\sqrt{5}$ , which is 0.015. This was obtained using conservative assumptions for the purpose of sample size considerations in this exploratory study. Therefore, the estimated maximum half-width of a two-sided 95% confidence interval on the study sample average difference in proportion is approximately  $1.96 \times 0.015 = 0.031$ .

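### Does Section 11's general rule on change scales require the primary outcome to lead with relative rather than absolute change?

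*Combined protocol and SAP*

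**What the plan says.** The general paragraph of Section 11 covers all outcomes. For proportions its rule is "Changes will be defined as absolute differences for those outcomes where baseline distribution of proportion is close to 0 or 1". It gives no cut-off for closeness. For the remaining cases relative change comes first and absolute change second: "and relative (and absolute secondarily), changes otherwise". The same paragraph says that "outcomes will also be summarized on a per-subject basis for reporting", and that change outcomes are shown with the distribution of values at each contributing time point.

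The next paragraph deals with the primary outcome alone. It asks for 15 per-subject differences with their confidence intervals and for the proportion infected across subjects at each time point. It ends: "Finally, the average difference from week 0 to week 1 (absolute difference) for the study sample will be estimated and summarized".

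Section 10 uses the same scale. It introduces its precision calculation with "For the primary outcome of difference in proportion of HCV-infected hepatocytes between week 1 and baseline", says that "the average difference across the 5 subjects within each group will be calculated", and gives a 95% half-width for that average only. The primary objective (3.1) speaks of estimating a one-week change and names no scale.

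**The concern.** Sections 4.1 and 8.8 report that the team's laser-microdissection assay found 21-45% of hepatocytes infected, in four earlier subjects. Section 10 assumes 50%. On an ordinary reading neither is near 0 or 1, so the default would make relative change lead. The primary outcome is nonetheless defined, averaged and sized as an absolute difference, and nothing marks it as an exception. Two analysts could each cite Section 11 for a different headline.

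The choice could matter. Section 4.2 reports two coinfected participants, on another regimen, whose infected share was only 1% at Day 7. If residual infection is that low here, the absolute change almost repeats the Day 0 value and carries little information about clearance. Section 10 says that the design "will permit the comparison of the NS3/4 inhibition versus none", and likewise permits a comparison of coinfected with mono-infected participants. An insensitive headline would serve those comparisons poorly.

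**Working it through.** **The plan's own figure.** Section 10 takes p = 0.5, n = 400 cells per time point and 5 subjects.
- Within-subject SE = √(2 × 0.5 × 0.5/400) = 0.0354.
- SE of the average = 0.0354/√5 = 0.0158 (printed as 0.015).
- Half-width = 1.96 × 0.0158 = 0.031, as stated.

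This describes the absolute scale only.

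**How far absolute change repeats Day 0.** The ratio is (p0 − pt)/p0, where p0 is the Day 0 proportion and pt the on-treatment proportion.

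| Left on treatment | p0 = 21% | p0 = 33% | p0 = 45% |
|---|---|---|---|
| 1% | 95% | 97% | 98% |
| 10% | 52% | 70% | 78% |
| 15% | 29% | 55% | 67% |

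The insensitivity is real at 1% and fades as residual infection rises.

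**An assumed threefold gap, 1% v 3%, both from 33%.** Cells are treated as independent, n = 400.
- Absolute scale, 5 v 5. The per-subject variances are (0.33 × 0.67 + 0.01 × 0.99)/400 = 0.000578 and (0.33 × 0.67 + 0.03 × 0.97)/400 = 0.000626. Half-width = 1.96 × √(0.001203/5) = 3.0 points, against a gap of 2 points.
- If Day 0 is uniform over 21-45% (variance 0.24²/12 = 0.0048 per subject), the half-width is 1.96 × √((0.001203 + 0.0096)/5) = 9.1 points.
- log10 ratio with 0.5 added to the counts, using the 3 v 3 Day 7 biopsies. The exact binomial SDs are 0.234 and 0.130. Half-width = 1.96 × √((0.234² + 0.130²)/3) = 0.30, against a gap of log10 3 = 0.48. With the Day 0 spread (log10 SD 0.094 per subject) it is 0.34.

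On counting error alone the ratio looks better.

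**Does that advantage last?** Three checks say that it is conditional.

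1. *Clustering.* Section 8.8 reports that infected cells cluster. The documents give no design effect, so take 2 and 3 as assumptions. The counting half-width of 0.30 becomes 0.30 × √2 = 0.43 and 0.30 × √3 = 0.52, against the same 0.48. The absolute scale gets no better, but the ratio's clear lead has gone.
2. *Biopsy day.* Each group has 3 Day 7 and 2 Day 4 second biopsies. The table shows simulated power for 5 v 5 with an exact two-sided 5% rank test, and clearance proportional to the infected share (a model that favours ratios). The three entries are for between-subject SDs of 0.05, 0.10 and 0.15 per day.

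| Clearance per day | Biopsy days | Absolute | log ratio |
|---|---|---|---|
| 0.6 v 0.4 | separated | 7 / 7 / 8% | 81 / 54 / 34% |
| 0.6 v 0.4 | pooled | 5 / 5 / 6% | 10 / 13 / 11% |
| 0.6 v 0.5 | pooled | 3.3 / 3.6 / 3.7% | 0.2 / 1.1 / 2.0% |

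Most of the gain comes from separating the biopsy days, which is a different question from the scale. Pooling costs less when the slower group keeps 10-15% at Day 7. There, at SDs of 0.05-0.10, the pooled log ratio has 81-100% power against 37-77% for absolute change.

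3. *Form of clearance.* Suppose treatment removes a fixed number of points: 20 v 15 at Day 7 and 15 v 10 at Day 4, with SD 2 or 4 points and days separated. The absolute scale then has 43% / 25% power and the log ratio 28% / 20%, so the ranking reverses.

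Neither clearance model comes from the documents. The plan names no stratified test, so these powers only illustrate how the ranking moves.

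**What the plan already reports.** The on-treatment proportion is planned output. Under proportional clearance at 0.6 v 0.4 per day with days separated, it has 72 / 47 / 30% power, close to the log ratio's 81 / 54 / 34%.

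**The case for a change.** The strongest case for a change is that the document never says which sentence governs, and that a reader who can derive a ratio still does not know which result leads. The low range in Section 4.1 (1.7-21.6%) comes from another method, so it does not rescue the absolute scale under the rule. The only on-treatment figure quoted is 1%, exactly where absolute change is weakest. Settling the scale beforehand would cost a sentence, or a sentence and one precision line.

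The textual mismatch stands. So does the insensitivity at very low residual infection, and Section 10's 0.031 would not describe precision on a relative scale. It does not follow that the plan leaves its headline open. A default for all outcomes followed by a specific instruction for one outcome is normally read with the specific one governing, and Sections 10 and 11 agree on it. The trigger is also soft: there is no cut-off, and the baseline range rests on four people. Nor is a log ratio with 0.5 added simply the plan's own rule applied, since Section 11 says only relative change. An exempting sentence would tidy the text without altering any number reported.

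**Conclusion.** No change is needed. The primary scale is stated as the absolute difference, consistently in Sections 10 and 11. The unreconciled default is a drafting slip that an analyst would resolve the same way. Per-subject results and proportions at both time points are required, so nothing is lost to a reader who prefers ratios.

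The choice of lead scale is a fair trade-off. The absolute change is 95-98% of the Day 0 value if 1% of cells stay infected, but 29-67% if 15% do. The ratio's advantage rests on assumed proportional clearance, nearly independent cells and, in the 1% range, separated biopsy days. It reverses under additive clearance. The primary objective is estimation. Section 10 says that "this study is exploratory and is enrolling a very small sample" and makes no power claim, so sensitivity to group differences is not a standard that the headline must meet.

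This conclusion assumes that analysts follow the specific primary-outcome text and report the per-subject and time-point summaries as Section 11 asks.
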